## **2. Data Entry Methods**

Survey data will be collected on password-protected tablets and computers within the Center for Epidemiologic Research (CER) at the Brown University School of Public Health. The REDCap™ platform exceeds patient confidentiality and data security requirements for clinical trials and are both HIPAA compliant and fully validated for FDA 21 CFR Part 11.

### 3. Data Analysis Plan

For all analyses, a series of routine procedures will first be conducted to ensure data accuracy/adequacy. Descriptive statistics will provide examination of the variables' distributional properties; if required, data will be transformed to achieve normality. For all analyses, we will adopt an intention-to-treat (ITT) approach to address potential problems inherent in following only intervention completers (e.g., self-selection effects, differential attrition across groups). However, we will conduct a modified ITT (mITT), excluding participants who were randomized but did not receive the intervention. For all analyses, the PI, senior biostatistician, and team of co-investigators/consultants will remain blinded to the assignment of study groups until after the statistical analyses are complete and finalized; however, the PI and Project Director receive unblinded information regarding the primary outcome as they were reported by participants, since it is considered a severe adverse event (SAE) and thus these cases are reported to members of the members of the data safety monitoring board (DSMB) and the institutional IRB.

Prior to conducting statistical analyses described below, we will create two baseline tables: 1) one that compares prognostic characteristics between treatment groups immediately after randomization; and 2) a second that compares prognostic baseline characteristics between treatment groups, stratified by whether they completed both outcome visits, a single outcome visit, or were lost to follow-up (i.e., did not complete either the six or 12 month study visit).

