Experimental arm participants will receive the RAPIDS intervention, which includes education about the dangers of IMF, motivational interviewing to increase willingness to use fentanyl test strips and engage in overdose risk reduction behaviors, hands-on training to use the test strips, and opportunities to plan and role- play how to implement overdose risk reduction behaviors upon receipt of a positive or negative test result. In addition, intervention participants will receive ten test strips for personal use. Motivational interviewing “booster” sessions will occur at 1, 2, and 3 months post-randomization, with additional test strips provided on an as needed basis. In the attention-matched control arm, participants will receive standardized overdose education and naloxone distribution (OEND) training, with attention-control visits at 1, 2, and 3 months.

Participants in both arms will receive a naloxone kit after completion of the first session, and information regarding where to obtain additional naloxone at subsequent visits. Follow-up interviews will occur at 6 and 12 months. The primary endpoint will be the rate of self- reported overdose over the follow-up period. Secondary endpoints (e.g., accidental overdose death and suspected EMS runs for overdose) will be ascertained by data linkage to statewide overdose surveillance databases maintained by the research team. Consistent with recruitment rates in our prior studies, we aim to enroll 20 participants per month starting in Year 1 until target

enrollment is reached.

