**Behavioral Outcomes:** Participants in the intervention arm will be asked a series of questions regarding fentanyl test strip utilization at all follow-up assessments. These questions were used successfully in our pilot study, and include items such as, “Of the 10 tests we gave you, how many tests did you use?” and, “What did you do when you found out your drugs were laced with fentanyl?” As an additional measure of test strip utilization, participants will be asked to return unused tests to the study office. We will also assess motivations for using the test strips, including a desire to avoid IMF-contaminated drugs or purposely identifying fentanyl.

At each time point, participants will be asked about the practices they engage in to avoid accidental overdose. Strategies to avoid overdose include the target overdose risk reduction behaviors:

1. discarding IMF-contaminated drugs,
2. not using alone (and staggering drug use with another person who is able to administer naloxone and call 911 in the event of an overdose), and
3. keeping naloxone nearby.

We will also assess other harm reduction practices, including taking a “tester” or lower initial dose, avoiding injection drug use, and purchasing drugs from a consistent source.

**Standard of Care (Attention-Matched Control Arm).** Existing research suggests that training people who are at risk for overdose and their peers on how to respond when witnessing an overdose is a feasible and effective strategy for preventing overdose death. Given that this represents current overdose prevention practice, participants in the control arm will receive the standardized OEND training that occurs in Rhode Island. This program is based on the common components of many community-based overdose prevention interventions in the US, and includes information on risk factors for overdose, recognizing an overdose, performing rescue breaths, administering naloxone, and recommendations to call 911. **To ensure equivalent attention to the RAPIDS arm, control arm participants will return for retention visits at 1, 2, and 3 months,** and will answer a series of questions regarding substance use and overdose risk behaviors.

**Potential Moderators/Other Key Measures:** The RAPIDS survey instrument will contain additional behavioral, psychological, and clinical assessments asked of everyone in the study. Many of these questions have been piloted successfully in our prior research.

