**Two trained *Interventionist Research Assistants* (RAs) will manage the visits to [name]:**

- The first RA, *Research Assistant A*, will be responsible for the informed consent protocol and conducting the survey assessment with the participant. They will also be responsible for administering the RAPIDS intervention for participants randomized to the intervention, which includes the provision of 10 BTNX Rapid Test Strips for take-home, personal harm reduction use.
- The second RA, *Research Assistant B*, will be responsible for conducting the rapid drug screen with the participant. Participants will provide a urine sample for a 12-drug panel and fentanyl baseline urine screen.
- *Research Assistant B* will record the results of the urine screen using the participant number identifier; results will not be shared with the participant.
- *Research Assistant B* will be responsible for the collection and storage of dried blood spots using capillary finger-stick methods for the purposes of toxicology screening and future use related to substance use and infectious diseases, results of which will not be shared with the participant. *Research Assistant B* will complete required specimen collection logs detailing the date and quantity of dried blood spot specimens collected.

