In the event that a cell phone is lost, stolen, or otherwise not returned, the iPhone will be remotely wiped of data. At the end of the study, all encrypted cell phone data will be destroyed and all cell phones will be wiped of data and returned to Brown University's Computing & Information Services (CIS).

Enrollment and assessment will occur in two stages: First, potential participants will text message, email, or call a study hotline, at which point a study staff member will screen for eligibility. If eligible, the staff member will then schedule an interview at the Brown University School of Public

Figure 3: Study Recruitment

Brown University IRB Original Approval: 4/18/2019

Brown University IRB Amendment Approval: 11/22/2019

Brown University IRB Amendment Approval: 8/10/2020

Brown University IRB Amendment Approval: 10/15/2020

Brown University IRB Amendment Approval: 02/26/2021

Brown University IRB Continuing Review Approval: 03/18/2021

Brown University IRB Amendment Approval: 06/15/2021

Brown University IRB Amendment Approval: 09/01/2021

Brown University IRB Amendment Approval: 10/05/2021

Brown University IRB Amendment Approval: 11/09/2021

Brown University IRB Amendment Approval: 12/13/2021

Motivational interviewing booster sessions

Additional fentanyl test strips distributed as needed

Key Assessment visits

Additional fentanyl test strips distributed as needed

Health. At this time, all assessments will occur at our study offices, which are centrally located and easily accessible to members of the study population. In some circumstances, the interviews may occur at a semi-private location outside of BUSPH (ex. Public library study rooms, clinics or other community partner agencies) (see **Attachment I**, Safety Protocol, for field-based safety measures).

Randomization: Randomization: Participants will be randomized 1:1 using a randomization table generated in SAS by the study's Biostatistician, which will be operationalized using the Randomization Generator Module in REDCap. Randomization will be assigned during the baseline visit. Intervention allocations will be maintained in REDCap by authorized users only, such as the study Statistician, and revealed only through REDCap by prompts during the baseline survey visit and post-baseline visits (See **Figure 3**).

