#### **Data Entry Methods**

Survey data will be collected on password-protected tablets and computers within the Centers for Epidemiology and Environmental Health (CEEH) at the Brown University School of Public Health. The REDCap™ platform exceeds patient confidentiality and data security requirements for clinical trials, and are both HIPAA compliant and fully validated for FDA 21 CFR Part 11.

The project's Biostatistician will manage the REDCap™ database architecture, dataset storage, and all input/output (i.e., data transfer) regulations.

Brown University IRB Original Approval: 4/18/2019  
Brown University IRB Amendment Approval: 11/22/2019  
Brown University IRB Amendment Approval: 8/10/2020  
Brown University IRB Amendment Approval: 10/15/2020  
Brown University IRB Amendment Approval: 02/26/2021  
Brown University IRB Continuing Review Approval: 03/18/2021  
Brown University IRB Amendment Approval: 06/15/2021  
Brown University IRB Amendment Approval: 09/01/2021  
Brown University IRB Amendment Approval: 10/05/2021

Brown University IRB Amendment Approval: 11/09/2021  
Brown University IRB Amendment Approval: 12/13/2021

For all analyses, a series of routine procedures will first be conducted to ensure data accuracy/adequacy. Descriptive statistics will provide examination of the variables' distributional properties; if required, data will be transformed to achieve normality. For all analyses, we will adopt an intention-to-treat (ITT) approach to address potential problems inherent in following only intervention completers (e.g., self-selection effects, differential attrition across groups). Prior to examining intervention effects, we will first assess the success of randomization on pre-intervention characteristics using one-way analysis of variance (ANOVA), with intervention group as the predictor variable. The extent to which groups differ on baseline characteristics will determine whether any of these should be included as covariates in the primary analyses (see below). Missing covariate data will be handled using multiple imputation performed in two stages using chained equations that specify the conditional models for all of the variables with missing values.

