There are three major assessment points: baseline, acute outcome (6 months post-randomization), and longer-term outcomes measured at 12 months. At baseline, after reviewing the study protocols and undergoing informed consent, all participants will complete an assessment battery and will then be randomized to one of the two study conditions. At all assessment visits, we will use computer-assisted personal interviewing (CAPI) to conduct participant interviews, which will include a computer-assisted self-interview (CASI) component for the collection of sensitive or stigmatizing information (e.g., injection drug use).

---

 [https://cdn.ymaws.com/www.cste.org/resource/resmgr/ps/ps2022/Recommendations for EMS NFOO.pdf](https://cdn.ymaws.com/www.cste.org/resource/resmgr/ps/ps2022/Recommendations%20for%20EMS%20NFOO.pdf)

 <https://health.ri.gov/data/hospitalization/discharge/>

Stronghold computing environment: We will obtain a central storage service hosted by Brown University's Computing & Information Services (CIS) Stronghold project. Stronghold is a HIPAA-aligned (Health Insurance Portability and Accountability Act), secure computing environment developed for housing, sharing, and analyzing sensitive data. The project's Biostatistician will oversee the database architecture, dataset storage, and all input/output (i.e., RIDOH data transfer) regulations. Stronghold is a highly secure computer and storage Windows-exclusive environment for research needs that involve very sensitive data needing special handling, data usage agreements, etc. See section F1 (Trial Safety) for additional information about Stronghold security.

All Stronghold users must:

- Be approved by the Principal Investigator (PI), authorized in writing to Brown University Computing &
- Information Services (CIS);
- Complete appropriate training for working with sensitive data (e.g. CITI training);
- Be in compliance with all relevant Institutional Review Board protocols;
- Be in compliance with any data use agreements or other agreements governing the use of the data stored on Stronghold; and
- Complete an on-boarding process led by the PI or Senior Research Assistant, which includes a review of data security protocols and a guided walkthrough of accessing the Stronghold virtual environment.

Data Transfers – there are select methods to import data, including but not limited to:

- Select Rhode Island state agencies and other offices using a secure VPN tunnel

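### The SAP adds a modified ITT set whose exclusion, as worded, has no control-arm counterpart, and does not say whether it or the ITT set carries the primary result

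*SAP*

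**What the plan says.** SAP section 3 (Data Analysis Plan) opens with the general rule: "For all analyses, we will adopt an intention-to-treat (ITT) approach to address potential problems inherent in following only intervention completers". The next sentence, introduced by *However*, adds: "we will conduct a modified ITT (mITT), excluding participants who were randomized but did not receive the intervention". Receipt is not defined, no equivalent test is given for controls, and the role of the mITT is not stated. The Aim 1 text of the same section sets out the primary time-to-event analysis without naming its analysis set.

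The Data and Safety Monitoring Plan (protocol Attachment F, section C1) has the ITT sentence, "we will adopt an intention-to-treat (ITT) approach to address potential problems inherent in following only intervention completers", and no mITT.

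On what each arm receives, protocol 3.1b makes one research assistant "responsible for administering the RAPIDS intervention for participants randomized to the intervention". For controls, protocol 3.1a says "participants will receive standardized overdose education and naloxone distribution (OEND) training, with attention-control visits at 1, 2, and 3 months", and the standard-of-care paragraph of 3.1b says "participants in the control arm will receive the standardized OEND training that occurs in Rhode Island".

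On timing, protocol 3.1d says "Randomization will be assigned during the baseline visit". SAP section 1 says "all participants will complete an assessment battery and will then be randomized to one of the two study conditions". In Attachment A, however, the programmer note in Section 1d generates the allocation at screening, and Section 2a carries the arm over from the screener and shows it to the research assistant as the baseline survey opens.

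**The concern.** An mITT set is safe only if the exclusion cannot depend on the arm. Here the test is receipt of something that, in the protocol's usual terms, only the experimental arm is offered. A control who leaves before the overdose education session fails no stated test; an experimental participant who leaves before the strip training does. If those removed differ in overdose risk, the two groups are no longer comparable, and that is the self-selection the preceding sentence says ITT is there to prevent.

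A difference in risk is plausible. The Safety Protocol (Attachment I) allows a visit to be cut short, and it treats visible intoxication as a reason for concern. With two analysis sets and no stated order, it is also unclear which one answers the primary question.

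**Working it through.** **1. Which arm does the exclusion act on?** Three places use *intervention* for the experimental treatment only: the research-assistant duties in protocol 3.1b; the break for education/intervention in Attachment A, which routes the intervention arm to the RAPIDS section and controls elsewhere; and the Reopening Plan, where only some participants are randomised to a behavioural intervention session. The SAP's per-protocol analyses likewise select within the experimental arm and compare with all controls. Taken with full literalness the rule would remove every control, which cannot be meant. The natural working reading is removal from the experimental arm only.

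**2. Who would be removed?** The first session follows the baseline survey within the same visit. Under protocol 3.1d and SAP section 1, allocation is also made at that visit. The excluded are then people who leave between allocation and the session. If the arm is generated at screening, as Attachment A has it, randomised no-shows are possible as well, in either arm. Neither their number nor their risk is given.

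**3. Reproducing the plan's power figure** (SAP section 6: 250 per arm, 80% retention, 20% against 10%; two-sided 0.05 from section 4).

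- Evaluable per arm: 250 × 0.80 = 200.
- Power = Φ[(0.10·√200 − 1.96·√(2·0.15·0.85)) / √(0.20·0.80 + 0.10·0.90)] = Φ[(1.4142 − 0.9897)/0.5] = Φ(0.849) = 80.2%, matching the stated >80%.
- Required number: 199 evaluable per arm, and 199/0.80 gives 249, matching 250.

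**4. Effect of a one-arm exclusion when the intervention does nothing.** Both arms have 20% risk as randomised. A share f of the experimental arm, with risk pₑ, is removed; f and pₑ are assumptions.

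- Remaining experimental risk: p = (0.20 − f·pₑ)/(1 − f). Risk ratio: p/0.20.
- Chance of a significant result favouring the intervention: Φ[(d − 1.96·SE₀)/SE₁], where d = 0.20 − p, SE₀ is the pooled and SE₁ the unpooled standard error, with 200 controls and 200(1 − f) experimental participants.

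Worked case, f = 10%, pₑ = 40%: p = (0.20 − 0.04)/0.90 = 0.1778 and the risk ratio is 0.89. With 180 against 200, the pooled risk is 72/380 = 0.1895, SE₀ = 0.0403 and SE₁ = 0.0402. Then Φ[(0.0222 − 0.0789)/0.0402] = Φ(−1.41) = 7.9%.

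| Excluded (f) | Risk of excluded (pₑ) | Remaining risk | Risk ratio | False benefit (nominal 2.5%) |
|---|---|---|---|---|
| 1% | 40% | 19.8% | 0.99 | 2.8% |
| 2% | 40% | 19.6% | 0.98 | 3.2% |
| 5% | 30% | 19.5% | 0.97 | 3.4% |
| 5% | 40% | 18.9% | 0.95 | 4.5% |
| 10% | 40% | 17.8% | 0.89 | 7.9% |
| any | 20% | 20.0% | 1.00 | 2.5% |
| 10% | 10% | 21.1% | 1.06 | 1.3% |

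This is an unadjusted two-proportion approximation to a planned survival analysis that adjusts for baseline covariates.

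**5. After the change.** ITT in all randomised participants restores a risk ratio of 1.00 and a 2.5% false-benefit rate. A rule applied identically to both arms does the same, provided failure to start the session does not itself depend on the arm.

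**The case against.** The case on the other side has real force.

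- **The one-arm reading is not certain.** A reader might infer that only the experimental arm can fail the test. Usage varies: protocol 3.1d speaks of intervention allocations and assignment for both arms, and the Reopening Plan speaks of an intervention session for every participant. Controls have a defined first session they could equally miss. The SAP may simply mean the assigned condition, but it does not say so.
- **Early drop-outs are not what the rule removes.** A reader might infer that everyone who stops early leaves the experimental arm. At 20% excluded with 40% risk that would give a risk ratio of 0.75 and a 23.0% false-benefit rate. The documents do not support this: anyone who completes the baseline visit has had the first session, and attendance at months one to three has its own per-protocol analysis. The session is also short, about 15 minutes in the Reopening Plan, so few should be lost.
- **The direction is not fixed.** A reader might infer that the bias must favour the intervention. It does so only if those removed are at higher risk.
- **ITT is not displaced.** It is adopted for all analyses, the monitoring plan names it for the primary endpoint, and the primary-endpoint text never mentions the mITT.
- **Adjustment helps.** Overdose history, injection, housing instability and prior emergency records are covariates and should absorb some of any imbalance.

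All of this limits the size of the point. None of it supplies the missing definition, the control-arm rule or the order of the two sets.

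**Conclusion.** The point holds in a limited form. The SAP specifies a post-randomisation exclusion that, on its most natural reading, applies to one arm, and it leaves the role of the resulting set open. Two analysts could build different mITT sets from the same sentence.

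The likely size is small: at 1% to 2% excluded with double the average risk, the risk ratio moves to 0.99 to 0.98 and the false-benefit rate to 2.8% to 3.2%. It becomes material at around 5% to 10% excluded at that risk (4.5% to 7.9%), disappears at equal risk and reverses at lower risk. The documents give no exclusion rate and no risk for those excluded, so these figures are a range of consequences, not a forecast. They assume a one-arm exclusion, 20% risk, 200 evaluable per arm and no covariate adjustment. The documents do not support concluding that the mITT will favour the intervention, or that it replaces ITT.

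**What to change.** In SAP section 3:

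1. State that the primary time-to-event analysis is ITT, in all randomised participants, by assigned arm, whatever session content they received.
2. Keep the mITT only as a labelled sensitivity analysis. Define receipt as starting the assigned baseline session, RAPIDS or overdose education, and apply that test identically in both arms.
3. Report the number excluded, by arm.
4. Reconcile when the arm is generated and who sees it, across protocol 3.1d, SAP section 1 and Attachment A Sections 1d and 2a, so that it is clear whether randomised no-shows can exist.

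A rule based on leaving before the arm is revealed would be harder to apply, because Section 2a shows the arm to the research assistant at the start of the survey. Even a symmetric rule remains a post-randomisation exclusion, so it should not carry the primary claim.

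The cost is a few sentences and an mITT that lies closer to the ITT result. No planned analysis is lost.

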#### Assessing intervention efficacy in reducing fatal and nonfatal overdose (Aim 1, primary endpoint).

The primary outcome will be **non-fatal overdose**, defined as a composite outcome, consisting of one of the following:

1. A self-reported overdose ascertained at the six and/or 12 month follow-up visits;
2. A non-fatal opioid overdose identified in the Rhode Island EMS database, using a case definition for suspected overdose developed by RIDOH previously;
3. An emergency department encounter for an accidental drug overdose that did not result in death, using a case definition developed by the CDC;

The primary analysis will be conducted using a survival framework, with time to *first* nonfatal overdose—identified through any of the data sources noted above—serving as the primary outcome. For self-reported data, event times will be estimated from SAE reports (in which participants are asked to estimate the date of their overdose). Participants will be right-censored as of the date of the first

---

 <https://www.ncbi.nlm.nih.gov/pmc/articles/PMC7948191/>

outcome event or at the end of the follow-up period, defined as 15 months following the participant's baseline visit.

To account for potential imbalance and to improve statistical efficiency, we will adjust for known or anticipated prognostic variables measured at baseline. These variables will include sociodemographic characteristics (e.g., age, gender identity, race/ethnicity), recent criminal justice involvement, housing instability, and substance use patterns including injection drug use & history of overdose. Variables will be transformed or categorized as necessary to address skewed or imbalanced data. We will also adjust for pre-baseline EMS runs for suspected opioid overdoses and ED encounters for drug overdoses using the case definitions noted above, occurring up to six months prior to the date of the participant's baseline visit.

At the completion of the study, patterns of data missingness will be explored to determine the appropriate assumptions required for each affected variable. Missing covariate data considered to be missing completely at random (MCAR), missing at random (MAR) and/or missing not at random (MNAR) will be handled using multiple imputation in SAS (proc MI procedure). Performed in two stages using chained equations, the model will specify the conditional models for the missing outcome and covariates as "MCAR", "MAR", or "MNAR". First, missing patterns will be tested. Then, imputing procedures will be separated into an "imputation phase", "analysis phase" and a "pooling phase". Finally, models with complete case, available data, and fully imputed data will be compared based on their coefficients, standard errors (SE), and *p*-value for the covariates included in the model.

To examine the effect of missing self-reported outcome data on the results, we will first examine the concordance between the self-reported outcome and the primary endpoints relying on administrative data linkages. If a high degree of correlation is observed (e.g.,  $r > 0.80$ ), we will assume missing self-reported outcome information has a negligible impact on the results. If a lack of concordance is observed, we will conduct stratified analyses by number of completed outcome visits (e.g., zero, one, and two) and also employ imputation-based procedures as noted above.

Second, in an exploratory analysis, we will determine the effect of the intervention on the more severe overdose endpoints, defined as an EMS run for suspected overdose, an ED encounter for drug overdose, or drug overdose death. An unintentional fatal overdose (involving any substance) will be determined through linkage to the Office of the State Medical Examiner (OSME), which is responsible for investigating all accidental deaths. Specifically, as defined previously, cases will be considered confirmed unintentional drug-related overdose fatalities if: (i) the death was pronounced in Rhode Island; (ii) the final manner of death was deemed an accident by the medical

---

 <https://doi.org/10.1016/j.drugpo.2017.05.029>

examiner, and (iii) a drug is listed on the death certificate as the primary cause of death or a significant contributing factor. This analysis will be conducted using the same methodology as described above.

In two per-protocol sub-analyses, we will determine the effect of the intervention on the primary study endpoint among those who: (1) reported using fentanyl test strips during at least one intervention visit (months one, two, and three) compared to all participants assigned to the control arm; and (2) participants who completed one, two, and all three intervention visits using an ordinal variable, compared to all participants assigned to the control arm.

Finally, to account for potential treatment contamination (e.g., use of fentanyl test strips in the control arm, lack of use in the treatment arm), we will employ an instrumental variable approach to estimate the contamination-adjusted intention to treat (CA ITT) effect. We will consider 'receipt of treatment' to be self-reported use of fentanyl test strips at months one, two, or three follow-up visits.

Examine whether the treatment effect is mediated by differential uptake of risk reduction behaviors in the intervention arm (Aim 2). If the RAPIDS intervention shows efficacy in reducing overdose rates among the sample (Aim 1), we will explore the extent to which this relationship works through several possible mediators. For mediation analyses, first, we will examine, in multivariable regression models, which mediators, if any, are significantly changed by the intervention (i.e., the rate of change differed by treatment assignment). For those that are significantly impacted by the intervention, we will conduct path analysis using structural equation modeling to determine whether the effect of the intervention on overdose was through the hypothesized mediator(s). Structural equation modeling (SEM) allows for the simultaneous estimation of total, direct, mediated and indirect effects of a causal variable (i.e., the intervention) on the outcome (i.e., overdose) through a set of mediator variables. SEM can handle outcomes and mediators with a variety of distributions (including, Gaussian, Poisson and Binomial). Inferences for indirect effects can be estimated using bootstrapped confidence intervals.

Determine whether intervention efficacy varies across participant subgroups (Aim 3). This is an exploratory aim. We will examine if heterogeneity of intervention effect is modified by key baseline characteristics of interest, including: age; sex; type, frequency, and route of drug use; baseline level of overdose risk (e.g., lifetime history of overdose); and pre-intervention motivations for fentanyl test strip utilization. We will perform stratified subgroup analyses to determine if treatment effects vary between groups of individuals.

---

 [10.1136/bmj.c2073](https://doi.org/10.1136/bmj.c2073)

